2.2.1.3. Safety Pharmacology and Toxicology

• Safety Pharmacology

Respiratory system: Sprague Dawley rats were continuously monitored for 3 hours (12.5, 50, and 200 mg/kg) for at least 6 hours, and no significant drug-related changes were observed in the respiratory parameters. After a single oral gavage of Sprague Dawley rats, 3D185 12.5 mg/kg, 50 mg/kg and 200 mg/kg, no significant effect on the central nervous system was observed.

Cardiovascular system: conscious Beagle dogs were monitored for at least 24 consecutive hours after single-dose oral gavage of 3D185 (5, 20 and 60 mg/kg), and no significant drug-related change in electrocardiogram, blood pressure and body temperature were observed.

Central nervous system: Sprague Dawley rats were given 3D185 12.5 mg/kg, 50 mg/kg and 200 mg/kg in a single oral gavage, and no significant effect on the central nervous system was observed.

• Reproductive and Developmental Toxicity

After oral dose of 3D185 at 30, 10 and 3 mg/kg from GD6 to GD15 in pregnant Sprague Dawley rats, the no-observed-adverse-effect-level (NOAEL) in pregnant rats was 30 mg/kg/day. And the NOAEL for embryo-fetal development was 3 mg/kg. No significant toxicity changes were observed in the clinical symptoms, body weight and food consumption of pregnant rats in each dose group. There were no significant drug-related changes in embryonic development and fetal appearance, visceral and bone examinations in the 3 mg/kg group.

• Single-Dose Toxicity

Sprague Dawley rats were given 200, 1000 and 2000 mg/kg 3D185 by single oral gavage. Both male and female animals were well tolerated, and the MTD was greater than 2000 mg/kg.

Beagle dogs were given 50, 250 and 1000 mg/kg 3D185 by single oral gavage and were tolerated by both male and female animals. The main toxicity is mild gastrointestinal symptoms and elevated PHOS. The MTD is greater than 1000 mg/kg.

• Repeat-Dose Toxicity

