- 4. CBC with differential: whole blood count (absolute value) includes red blood cell count, white blood cell counts, and differential counts (neutrophils, lymphocytes, monocytes, eosinophils, and basophils), platelet count, hemoglobin, and hematocrit. This test should be completed within 7 days prior to the first dose. It is unnecessary to repeat on C0D1 if the subject has no clinical signs and indications. This test should be completed before dosing within 3 days prior to days C1D1, C1D8, C1D15, C1D28, C2D15, C2D28, CxD28, and safety follow-up period. An unscheduled exam can be performed if there are clinical indications.
- 5. Blood biochemistry includes ALT, AST, total bilirubin, BUN (urea nitrogen) or urea, Cr (creatinine), blood glucose, potassium, sodium, chlorine, calcium, phosphate, magnesium, total protein, albumin, albumin/globulin ratio, LDH (lactate dehydrogenase), and ALP (alkaline phosphatase). This test should be completed within 7 days prior to the first dose. It isn't required to repeat on C0D1 if the subject has no clinical signs and indications. This test should be completed before dosing within 3 days prior to days C1D1, C1D8, C1D15, C1D28, C2D15, C2D28, CxD28 and safety follow-up period. Among them, phosphate levels will also be used for PD analysis.
- 6. Coagulation functions include prothrombin time (PT), APTT, and INR. This test should be completed within 7 days prior to the first dose. It isn't required on C0D1 if the subject has no clinical signs and indications. This test should be completed before dosing within 3 days prior to C1D28, every 8 weeks (±7 days) in additional cycles, and safety follow up visit.

- 7. Urinalysis includes specific gravity, pH, white blood cells, red blood cells, proteins, glucose, ketones, and casts. This exam should be completed within 7 days prior to the first dose. If urine protein ++, it is recommended to test 24-hour urine protein quantitation as soon as possible (if within 72 hours). It isn't required on C0D1 if the subject has no clinical signs and indications. This test should be completed before dosing within 3 days prior to days C1D1, C1D8, C1D15, C1D28, C2D15, C2D28, CxD28, and safety follow-up period.

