- 8. The 12-lead ECG should be completed within 7 days of the first dose. This test should be performed at 2 hours (±5 min) after dosing on C0D1 and C1D28. It also should be completed before dosing within 3 days prior to days C1D1, C1D8, C1D15, C2D15, C2D28, CxD28, and safety follow up visit.
- 9. Ophthalmological examination includes non-contact intraocular pressure, slit lamps, fundus examinations, and optical coherence tomography. The examination should be completed within 7 days prior to the first dose. It isn't required on C0D1. This test should be completed before dosing within 3 days prior to C1D28, every 8 weeks (±7 days) in additional cycles, and the safety follow-up period.
- 10. A serum pregnancy test should be completed at the screening period. Female subjects at childbearing age should complete the examination within 7 days prior to the first dose.
- 11. Echocardiography should be performed during the screening period, the treatment period (if clinically indicated), and the safety follow-up period.
- 12. Baseline tumor assessment should be completed within 28 days prior to the first dose. It is recommended to perform CT or MRI of the chest, abdomen, and pelvic at baseline. Subjects with known or suspected brain metastases should have a CT or MRI of the brain at baseline. If there are clinical indications or suspicious lesions in other areas, tumor imaging evaluation must also be performed. Baseline assessment and post-treatment efficacy assessment will be performed using the same method and as much as possible by the same Investigator (RECIST 1.1 criteria). Tumor imaging assessment (CT or MRI) should be performed every 8 weeks (#7 days) from C1D1 until disease progression, death, withdrawal of informed consent, or termination of treatment. Subjects who discontinue treatment for reasons other than disease progression or death should continue with imaging assessments per protocol-defined schedule until disease progression, death, or withdrawal of informed consent, whichever occurs first. If the imaging result shows a CR or PR for the first time, it is necessary to repeat the tumor imaging at least 4 weeks later to confirm the response. If clinically indicated, the Investigator can perform an unscheduled tumor assessment.

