4.4. Rationale for Selection of the Starting Dose

Per FDA/CFDA guidelines, the clinical starting dose for molecular targeted drugs should be selected by the approach of converting preclinical NOAEL dose to a human equivalent dose based on body surface area. The safety factor should then be considered. Based on the result of preclinical repeat-dose toxicity study of 3D185, the NOAEL in rats was 10 mg/kg. The human starting dose was estimated by 1/3 NOAEL dose of the rat, which was approximately $1/3 \times 10$ mg/kg $\times 0.162 \times 60$ kg = 32.4 mg.

Per ICH guideline S9, it is typically used body surface area for interspecies dose conversion to select the starting dose for most systemically administered small molecule drugs. A common practice is to use $1/10 \text{ STD}_{10}$ (Severely Toxic Dose in 10% animal) in rodents as the starting dose. If non-rodent is the closely related species, then 1/6 HNSTD (Highest Non-Severely Toxic Dose) can be selected as the starting dose. Based on the preclinical repeat-dose toxicity study of 3D185, the HNSTD in dogs was 12 mg/kg. The human initial dose was estimated by 1/6 NOAEL dose of the dogs, which was approximately $1/6 \times 12 \text{ mg/kg} \times 0.541 \times 60 \text{ kg} = 64.92 \text{ mg}.$

In comparison, a relatively safer dose will be selected. Considering the strength of the drug, the starting dose of 3D185 for the clinical trial will be 25 mg orally once a day.

Based on the existing preclinical data, 3D185 will start at the dose of 25 mg by using the combination of accelerated titration and i3+3 for dose-escalation^[1]. The seven dose-escalation cohorts are 25 mg, 50 mg, 100 mg, 150 mg, 200 mg, 250 mg, and 300 mg, respectively. The preset dose cohorts may be adjusted during this study. The decision of the actual dose will be made by the Investigators and the Sponsor.

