- 12. Subjects who have symptomatic brain metastases or spinal cord compression. For the subjects, who have previously treated for brain metastases, if the clinical condition is stable and imaging evidence does not show disease progression within 4 weeks prior to the first dose, and do not need corticosteroid treatment within 2 weeks prior to the first dose, can enroll.
- 13. Subjects who have active bacterial or fungal infections (CTCAE Grade ≥ 2) that required systemic treatment within 14 days prior to the first dose.
- 14. Subjects who have active HBV infection (HBV DNA \geq 1000 copies/mL) and/or HCV antibody testing positive;
- 15. Subjects who have clinically significant cardiovascular diseases that occurred 6 months prior to first dose. Cardiovascular diseases include, but not limited to follows: acute myocardial infarction; severe/unstable angina; cerebrovascular accident or transient ischemic attack; congestive heart failure (NYHA > Class II, see Appendix 3); arrhythmias that require antiarrhythmic treatment except for beta blockers or digoxin; repeated ECG with QTc interval > 450 ms; high blood pressure that cannot be controlled by antihypertensive drugs (systolic blood pressure > 150 mm Hg, diastolic blood pressure > 100 mmHg).
- 16. Subjects who have clinically significant abnormal serum electrolyte levels.
- 17. Subjects who are receiving warfarin (low-dose warfarin up to 2 mg/day is allowed); or receiving antiplatelet anticoagulant therapy (aspirin at dose ≥ 300 mg/day, clopidogrel at dose ≥75 mg/day).
- 18. Female subjects in pregnancy or lactation. Male subjects or female subjects at reproductive ages who are unwilling to receive effective contraceptive measures.
- 19. Subjects who are judged by the Investigator to be unsuitable for this study.

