5.4.2. Subject Withdrawal/Discontinuation

If a subject has any medical condition and the Investigator believes that his or her continued participation in the study may jeopardize the safety, the Investigator has the right to decide that the subject will discontinue the study treatment early. All subjects, who signed the ICF and screened eligible into the trial, have the right at any time to withdraw or discontinue from the treatment of investigational product. In addition, a subject may be withdrawn by the Investigator if he/she violates the study plan or management and/or other safety reasons.

When a subject discontinues/withdraws prior to study completion, all applicable activities scheduled for the safety follow-up visit should be performed. Any drug-related AEs which are present at the time of discontinuation/withdrawal should be followed in accordance with the safety requirements.

During the treatment period, subjects can receive 3D185 treatment until one of the following events occurs:

- Subject withdrew consent;
- Progressive disease;
- Death;
- Unacceptable treatment toxicity;
- Start other anti-cancer therapy;
- The Investigator determines it is in the best benefit of the subject to discontinue the investigational product treatment;
- Poor compliance or severe protocol violations, and have an impact on drug tolerance, safety, or PK evaluation;
- Pregnancy during the treatment period;
- Lost to follow-up;
- Others.

Subjects who stop treatment prior to the documentation of disease progression will undergo repeated imaging for tumor response assessments at the frequency according to protocol until unequivocal disease progression is documented or the subject starts new anticancer therapies or subject withdraws consent from the trial, whichever occurs first. Subjects who withdraw from the study for clinical or symptomatic deterioration before objective documentation of disease progression. Every effort will be made to confirm a clinical diagnosis of disease progression by imaging.

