7.4.1.2. Safety Assessments

Safety assessments include AEs, physical examination, laboratory evaluations (CBC with differential, serum chemistry, coagulation, urinalysis, and pregnancy test), vital signs (blood pressure, heart rate, respiratory rate, body temperature), 12-lead ECG, echocardiography, and ophthalmologic examination (non-contact intraocular pressure, slit lamps, fundus examinations, and optical coherence tomography). An unscheduled exam can be performed if there are clinical indications. For detailed visit arrangement, please refer to Table 3 study flow chart.

Safety laboratory evaluations, including CBC with differential, serum chemistry, urinalysis, etc. will be performed by the site's local laboratory.

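### Serum β-hCG is tested once before the first dose and never again, although daily dosing is open-ended and pregnancy is a mandatory stopping event

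*Protocol*

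**What the plan says.** Every place in the protocol that sets the schedule gives the same answer.

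- Table 3 has one mark for serum β-hCG, in the Days -7 to -1 column.
- Note 10 to Table 3 reads "A serum pregnancy test should be completed at the screening period" and sets a 7-day window before the first dose for women of childbearing age. Section 7.1 agrees.
- The visit lists in 7.3.1 to 7.3.4 and the itemised safety follow-up list in 7.3.5 contain no pregnancy test.
- Section 7.4.1.2 counts the test among the "laboratory evaluations (CBC with differential, serum chemistry, coagulation, urinalysis, and pregnancy test" and refers to Table 3 for timing. The other four are repeated on treatment and at follow-up. For the blood count, for example, note 4 says "This test should be completed before dosing within 3 days prior to days C1D1, C1D8, C1D15, C1D28, C2D15, C2D28, CxD28, and safety follow-up period". Note 5 names the same visits for serum chemistry.

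The related safeguards are these. Exclusion 18 in 5.3 bars "Male subjects or female subjects at reproductive ages who are unwilling to receive effective contraceptive measures". Section 5.4.2 lists "Pregnancy during the treatment period" as a reason to stop treatment. Section 8.4.7 requires immediate discontinuation and a report to the sponsor within 24 hours, and it also makes pregnancies within 28 (±7) days of the last dose reportable. Section 7.4.1.2 adds that "An unscheduled exam can be performed if there are clinical indications".

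On the nonclinical side, 2.2.1.3 gives a maternal NOAEL in rats of 30 mg/kg/day. It continues: "And the NOAEL for embryo-fetal development was 3 mg/kg".

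**The concern.** The protocol makes pregnancy an event that must stop treatment and be reported, but after the first dose it schedules nothing that would detect one. Dosing continues daily until progression, death, unacceptable toxicity or withdrawal of consent, so the time since the only test has no upper limit.

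The listed safeguards do not close this gap. The contraception criterion is a statement of willingness checked at entry. The unscheduled examination needs a clinical indication. The stopping and reporting rules begin only once the pregnancy is known. An unsuspected pregnancy can therefore continue under exposure until symptoms or the subject reveal it, and the stopping rule and the 24-hour report then start late.

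The rat data add weight, because the embryo-fetal no-effect level lies below doses that caused no adverse effect in the dams. Maternal signs cannot be relied on as a warning.

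**Working it through.** **Scheduled tests.** Screening: 1. Treatment visits: 0. Safety follow-up: 0.

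**Time since the test and doses taken.** Section 4.3 places the single-dose PK period on Days 1–7, so C0D1 is Day 1 and C1D1 is Day 8. C1D28 is then Day 35, which matches the 35-day DLT window. With 28-day cycles, C2D28 is Day 63 and C4D28 is Day 119. The test may be 7 days old at the first dose, and no missed doses are assumed.

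| Visit | Days since test (at most) | Scheduled doses |
|---|---|---|
| C1D1 (Day 8) | 7 + 7 = 14 | 1 + 1 = 2 |
| C1D28 (Day 35) | 7 + 34 = 41 | 1 + 28 = 29 |
| C2D28 (Day 63) | 7 + 62 = 69 | 1 + 2 × 28 = 57 |
| C4D28 (Day 119) | 7 + 118 = 125 | 1 + 4 × 28 = 113 |

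**Rat signal.** The tested doses were 3, 10 and 30 mg/kg. The ratio of maternal to embryo-fetal NOAEL is 30 / 3 = 10.

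**Human equivalents by the protocol's own conversion.** Section 4.4 states: "The human starting dose was estimated by 1/3 NOAEL dose of the rat". Its figure reproduces: 1/3 × 10 × 0.162 × 60 = 32.4 mg. The same factors, without the safety factor of 1/3, give:

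| Rat dose | Conversion | Planned levels above it (25, 50, 100, 150, 200, 250, 300 mg) |
|---|---|---|
| 3 mg/kg (embryo-fetal NOAEL) | 3 × 0.162 × 60 = 29.16 mg | 6 of 7 |
| 10 mg/kg | 10 × 0.162 × 60 = 97.2 mg | 5 of 7 |
| 30 mg/kg | 30 × 0.162 × 60 = 291.6 mg | 1 of 7 |

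Section 2.2.1.3 states neither the fetal finding nor the lowest dose at which it occurred, so the last two rows are a range for the unknown effect level. On the usual reading of a NOAEL the next tested dose, 10 mg/kg, would be the effect level, but the protocol does not say so.

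**The case against.** The schedule is internally consistent, so this is a question of how often to test, not a contradiction. It bears on no endpoint, analysis set or dose-finding rule.

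The protocol also has scheduled contacts that do not depend on symptoms: open questions about medical problems (8.3.2), a full physical examination at each listed visit from C1D1, and CT or MRI every 8 weeks, first at C2D28, with the pelvis recommended at baseline. The tenfold ratio compares the highest tested dose with the lowest, so dose spacing fixes it and it does not measure potency. The body-surface conversion serves in 4.4 to choose a starting dose; being above a NOAEL equivalent is not being above an effect level. Finally, subjects have pretreated advanced cancer and those unwilling to use contraception are excluded, so pregnancies will be few.

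Much of this is fair. The ratio and the dose counts are context and do not size the risk, and the number of pregnancies is probably small. But the scheduled contacts are not pregnancy tests. The questions do not ask about pregnancy, and imaging of the pelvis is only recommended. None of them is a substitute for β-hCG.

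It is also fair that testing which starts only at C1D28 leaves a first gap of up to 41 days, which is a reason to include C1D1.

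**Conclusion.** The concern holds. One test is scheduled, none after the first dose, and the time since that test grows without limit: up to 69 days at C2D28 and 125 days at C4D28.

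The protocol does not give the number of women of childbearing potential, so expected pregnancies cannot be calculated. The nature of the fetal effect and its threshold are not stated either, so nothing here demonstrates human harm. The case rests on a nonclinical signal that the protocol itself reports, on open-ended exposure, and on stopping and reporting rules that depend on a detection step nobody has scheduled.

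The change should be made for subject safety. Sample size, the i3+3 decisions and MTD selection are unaffected. Because this is a visit-schedule matter, it belongs in the protocol and is not something to leave to an SAP.

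**What to change.** Amend Table 3, note 10, 7.3.2 to 7.3.4 and 7.3.5. For women of childbearing potential, add β-hCG at each cycle's D28 visit and at the 28-day safety follow-up, and preferably at C1D1 before daily dosing starts. With C1D1 included, the early gap of up to 41 days splits into at most 14 days before C1D1 and 27 days from there to C1D28. After C1D28 the untested interval on treatment is about 28 days. Monthly testing shortens undetected exposure but does not prevent it.

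The cost is one more local-laboratory analyte at visits where serum chemistry is already drawn, plus the amendment. The share of women of childbearing potential is not in the protocol. Assuming 10–30% of 42 subjects gives 4 to 13 women. Treatment to C2D28 then means 3 extra tests each (C1D28, C2D28, follow-up), or 4 × 3 = 12 to 13 × 3 = 39 in all. With C1D1 it is 4 × 4 = 16 to 13 × 4 = 52. The chemistry sample volume is not stated, so a little more blood may be needed.

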4.4. Rationale for Selection of the Starting Dose

Per FDA/CFDA guidelines, the clinical starting dose for molecular targeted drugs should be selected by the approach of converting preclinical NOAEL dose to a human equivalent dose based on body surface area. The safety factor should then be considered. Based on the result of preclinical repeat-dose toxicity study of 3D185, the NOAEL in rats was 10 mg/kg. The human starting dose was estimated by 1/3 NOAEL dose of the rat, which was approximately $1/3 \times 10$ mg/kg $\times 0.162 \times 60$ kg = 32.4 mg.

Per ICH guideline S9, it is typically used body surface area for interspecies dose conversion to select the starting dose for most systemically administered small molecule drugs. A common practice is to use $1/10 \text{ STD}_{10}$ (Severely Toxic Dose in 10% animal) in rodents as the starting dose. If non-rodent is the closely related species, then 1/6 HNSTD (Highest Non-Severely Toxic Dose) can be selected as the starting dose. Based on the preclinical repeat-dose toxicity study of 3D185, the HNSTD in dogs was 12 mg/kg. The human initial dose was estimated by 1/6 NOAEL dose of the dogs, which was approximately $1/6 \times 12 \text{ mg/kg} \times 0.541 \times 60 \text{ kg} = 64.92 \text{ mg}.$

In comparison, a relatively safer dose will be selected. Considering the strength of the drug, the starting dose of 3D185 for the clinical trial will be 25 mg orally once a day.

Based on the existing preclinical data, 3D185 will start at the dose of 25 mg by using the combination of accelerated titration and i3+3 for dose-escalation^[1]. The seven dose-escalation cohorts are 25 mg, 50 mg, 100 mg, 150 mg, 200 mg, 250 mg, and 300 mg, respectively. The preset dose cohorts may be adjusted during this study. The decision of the actual dose will be made by the Investigators and the Sponsor.

4.5. Dose Limiting Toxicity (DLT) Definition

A DLT is defined as the occurrence of any of the following toxic reactions that are considered to be causally related to 3D185 by the PI within the first 35 days after the first dose.

- 1. Hematological toxicity:
 - 1. Grade 4 hematologic toxicity;
 - 2. Grade 3 febrile neutropenia (defined as ANC < $1,000/\text{mm}^3$, a single temperature of >

38.3 \mathbb{C} or a sustained temperature of \geq 38 °C for more than 1 hour) or Grade 3 neutropenia

lasts for more than 7 days with or without drug intervention;

3. Grade 3 thrombocytopenia with bleeding or require to platelet transfusion;

- 2. Non-hematologic toxicity:
 - 4. Any Grade ≥ 3 non-hematologic toxicity (except the following conditions that can be controlled by symptomatic treatment within 48 hours: nausea, diarrhea, vomiting, and electrolyte imbalance [except serum phosphorus]; Grade 3 fatigue with duration ≤ 7 days; Grade 3 hypertension that can be self-resolved or controlled by drugs to below 140/90 mmHg or baseline level within 72 hours);
 - 5. Serum phosphorus ≥7 mg/dL that is unable to recover to < 7 mg/dL within 14 days after phosphorus removal;
 - 6. With liver metastasis or baseline transaminase abnormalities: ALT/AST > 8 × ULN; without liver metastasis or baseline transaminase abnormalities: ALT/AST > 5 × ULN ;
 - 7. 3D185-related AEs that resulted in dose interruption of 3D185 for \geq 7 days in the first treatment cycle.

If the DLT is clinically recovered to Grade 0-1 within 28 days, the subject can resume the treatment of 3D185. If the subject can resume treatment, the Investigator may refer to the provisions of Section 6.3 (Precautions and Dose Modifications) for dose modifications to the same dose or reduce by one dose level.

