5.2. Inclusion Criteria

Subjects must meet all of the following criteria before they can be enrolled:

- 1. Age \geq 18 years.
- 2. Subjects must have a histological diagnosis of locally advanced or metastatic malignant solid tumors. Subjects must have failed the established standard treatment, or the standard treatment does not exist; or subjects are intolerant of or have refused to receive standard treatment. All subjects must have received at least one previous line of systemic treatment. Subjects with known genomic alterations for which there are approved therapies (e.g., ALK mutated NSCLC, microsatellite instability high/mismatch repair deficient solid tumors, EGFR NSCLC, etc.,) will have received such therapies prior to the enrolling in this study.
- 3. Subjects must have measurable or evaluable disease (according to RECIST 1.1, see Appendix 1);
- 4. ECOG Performance Status ≤ 2 .
- 5. Life expectancy ≥ 12 weeks.
- 6. Subjects must have normal levels of total serum calcium and total phosphate.
- 7. Subjects must have adequate organ and bone marrow function (subjects must not have received any hematopoietic growth factors, transfusion, or platelet within 1 week before the first dose).
 - CBC: neutrophils $\ge 1.5 \times 10^{9}$ /L, platelets $\ge 100 \times 10^{9}$ /L, hemoglobin ≥ 9.0 g/dL.
 - Liver function: total bilirubin $\leq 1.5 \times$ ULN, unless known to have Gilbert's disease; ALT/AST $\leq 2.5 \times$ ULN without liver metastasis; ALT/AST $\leq 5 \times$ ULN with liver metastasis;
 - Coagulation: $INR \le 1.5 \times ULN$ and $APTT \le 1.5 \times ULN$ (for subjects undergoing anticoagulant therapy, the Investigator should ensure that both INR and APTT are within the safe and effective treatment range).
 - Renal function: serum creatinine $\leq 1.5 \times \text{ULN}$, or creatinine clearance $\geq 60 \text{ mL/min}/1.73 \text{ m}^2$ in the condition of creatinine level > ULN; urine protein

analysis $\leq 1 + (\text{if } \geq 2+, 24 \text{ hours of urine protein test is required, if 24 hours urine protein <1 g, then allowed to enroll);$

- Adequate cardiac function: LVEF > 50% in two-dimensional echocardiography;
- 8. Subjects must have fully understood and voluntarily signed ICF for this study.

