In case of Grade 2 AST/ALT elevation in patients without liver metastasis or AST/ALT elevation \geq 3.0-5.0 folds over baseline value in patients with liver metastasis, withhold 3D185 until the level returns to grade \leq 1 or baseline, and the liver test should be evaluated at least twice a week. Restart treatment with 3D185 at the same dose level.

In case of total bilirubin ≥ 2 folds over ULN, withhold 3D185 until the level returns to CTCAE Grade ≤ 1 or baseline, and the liver test should be evaluated at least twice a week. Restart treatment with 3D185 at same dose level.

In case of Grade 3 AST/ALT elevation, subjects should withhold 3D185 until the AST/ALT level returns to CTCAE Grade ≤ 1 or baseline. If the AE resolves within 7 days, dosing may resume at the same dose level. If the AE resolves within 7-14 days, dosing may resume at the previous lower dose level or may be modified according to the Investigator's judgment. If the AE cannot resolve within 28 days, the treatment of 3D185 will be permanently discontinued. Liver enzymes should be monitored once a week when the subject receives 3D185 treatment again.

When a hepatic injury is suspected due to abnormal liver function test (such as Grade ≥ 3 AST/ALT elevation), it is recommended to perform a comprehensive assessment (liver imaging, liver function tests and pathogen tests, etc.) as soon as possible.

Abnormal values in AST and/or ALT concurrent with abnormal elevations in total bilirubin that meet the criteria outlined below in the absence of other causes of liver injury are considered

potential cases of drug-induced liver injury (potential Hy's law cases) and should always be considered important medical events, 3D185 must be discontinued immediately. The threshold of laboratory abnormalities for a potential case of drug-induced liver injury depends on the subject's individual baseline values and underlying conditions. Subjects who present with the following laboratory abnormalities (potential drug-induced liver injury) should be evaluated further to determine the etiology of the abnormal laboratory values definitively:

- Subjects with AST or ALT and total bilirubin baseline values within the normal range who subsequently present with AST or ALT values ≥ 3 folds over ULN concurrent with a total bilirubin value ≥ 2 folds over ULN with no evidence of hemolysis and an alkaline phosphatase value ≤ 2 folds over ULN.

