8.5. Assessment of Adverse Events

8.5.1. Assessment of Severity

The Investigator will make an assessment of severity for each AE and SAE reported during the study according to the NCI CTCAE Version 4.03.

In addition, the severity of each AE and SAE should also be assigned to one of the following categories:

- Grade 1: Mild; asymptomatic or mild symptoms; clinical or diagnostic observations only; intervention not indicated.
- Grade 2: Moderate; minimal, local or noninvasive intervention indicated; limiting age-appropriate instrumental activities of Daily Living (refer to preparing meals, shopping for groceries or clothes, using the telephone, managing money, etc.).
- Grade 3: Severe; severe medically significant but not immediately life-threatening; hospitalization or prolongation of hospitalization indicated; disabling; limiting selfcare activities of Daily Living (refer to bathing, dressing and undressing, feeding self, using the toilet, taking medications, and not bedridden.).
- Grade 4: Severe; Life-threatening consequences; urgent intervention indicated.
- Grade 5: Severe; Death related to AE.

The severity and seriousness of AEs should be distinguished. The severity is used to describe intensity which may not an SAE. For example, a headache may be severe in intensity, but not an SAE unless it meets the criteria for SAE.

The NCI CTCAE version 4.03 doesn't include the classification of hyperphosphatemia. The grade of hyperphosphatemia in this study is defined as: Grade 1: > ULN ~ 7 mg/dL; Grade 2: > 7 mg/dL ~ 9 mg/dL; Grade 3: > 9 mg/dL).

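### The DLT definition does not say whether the general Grade ≥3 rule or the separate 8×ULN limit governs transaminases in subjects with liver metastasis or abnormal baseline values

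*Protocol*

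**What the plan says.** Section 4.5 opens by combining its items disjunctively: "A DLT is defined as the occurrence of any of the following toxic reactions". Causality is judged by the principal investigator, and the window is 35 days from the first dose. Three of the non-hematologic items matter here, and the synopsis repeats all three.

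- **Item 4** is the general rule: "Any Grade ≥ 3 non-hematologic toxicity (except the following conditions that can be controlled by symptomatic treatment within 48 hours". The exceptions are nausea, diarrhea, vomiting, electrolyte imbalance other than phosphorus, short Grade 3 fatigue and controlled Grade 3 hypertension. Transaminases are not among them, and the item does not refer to item 6.
- **Item 6** is specific to transaminases and has two limbs: "With liver metastasis or baseline transaminase abnormalities: ALT/AST > 8 × ULN" and "without liver metastasis or baseline transaminase abnormalities: ALT/AST > 5 × ULN".
- **Item 7** makes a related AE a DLT if it interrupts dosing for 7 days or more in the first treatment cycle.

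Severity is graded "according to the NCI CTCAE Version 4.03" (Section 8.5.1). The protocol adds its own grades only for hyperphosphatemia and prints no ALT/AST limits for Grade 3. Section 5.2 admits subjects with "ALT/AST $\leq 5 \times$ ULN with liver metastasis". Section 6.3.1 requires dosing to be withheld for Grade 3 AST/ALT elevation until recovery to Grade 1 or baseline, without distinguishing subjects who have liver metastasis.

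**The concern.** A separate, higher limit for a named subgroup has a purpose only if lower elevations in that subgroup are meant not to count. Item 4, which excepts no transaminase elevation, counts every one that reaches Grade 3. The text does not say which item prevails, so either the 8×ULN limit does nothing or it conflicts with item 4.

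The situation is foreseeable. Section 6.3.1 names liver function abnormality as a possible toxicity of the drug, and Section 2.3 lists raised transaminases for similar drugs. Subjects with liver metastasis may enter close to the disputed range. The classification also matters statistically: DLT frequency is part of the primary endpoint (together with all AEs and SAEs), it is the numerator of the i3+3 decision, and it enters the isotonic estimate used to select the MTD (Section 4.2).

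**Working it through.** **Step 1. Where the two readings differ.** Let Grade 3 ALT/AST start above g×ULN. The value of g is an assumption. Item 6 suggests g = 5, because that is its limit for all other subjects. The sentence in Section 6.3.1 that begins "In case of Grade 2 AST/ALT elevation in patients without liver metastasis" pairs Grade 2 with a 3.0-5.0 fold rise, but that rise is over baseline, so it does not settle g as a multiple of ULN.

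For a subject with liver metastasis or abnormal baseline and a related peak of v×ULN:

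- item 4 gives a DLT if v > g;
- item 6 gives a DLT if v > 8;
- the readings disagree when g < v ≤ 8.

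With g = 5:

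| Peak (×ULN) | Item 4 | Item 6 | Readings differ |
|---|---|---|---|
| 4, 5 | no | no | no |
| 5.1, 6, 7, 8 | DLT | not reached | yes |
| 8.1, 10 | DLT | DLT | no |

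Range: at g = 3 the band is (3, 8], at g = 5 it is (5, 8], and at g = 8 it is empty. For illustration, a subject with liver metastasis who enters at 4.5×ULN and rises to 5.5×ULN is in the band at g = 5.

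**Step 2. What item 7 removes from the band.** Grade 3 elevation requires withholding (Section 6.3.1). If the interruption reaches 7 days in Cycle 1, item 7 makes it a DLT on either reading. What remains is mainly interruptions shorter than 7 days, or elevations that begin too late in Cycle 1 to accumulate 7 days. Short interruptions are possible because dosing may resume at return to baseline, and baseline may itself be high.

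**Step 3. Effect on the dose decision.** The plan's own interval reproduces from Appendix 8: 0.25 − 0.09 = 0.16 and 0.25 + 0.05 = 0.30. The Appendix 7 algorithm is: escalate (E) if x/n is below 0.16; stay (S) if it is inside the interval; if it is above 0.30, stay when (x−1)/n is below 0.16 and otherwise de-escalate (D).

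- 0/3 = 0, so E. 1/3 = 0.333 is above 0.30 and 0/3 is below 0.16, so S.
- 2/3 = 0.667 is above 0.30 and 1/3 is not below 0.16, so D.
- 0/6 = 0, so E. 1/6 = 0.167 is inside the interval, so S.
- 2/6 = 0.333 is above 0.30 and 1/6 = 0.167 is not below 0.16, so D.

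One subject counted under item 4 but not under item 6 therefore moves E to S (0/3 to 1/3, or 0/6 to 1/6) or S to D (1/3 to 2/3, or 1/6 to 2/6). The item 6 reading gives the lower count and favours escalation. The item 4 reading gives the higher count.

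**The case against.** The best reply is that there is no contradiction. Any one item suffices, item 6 nowhere says that lower elevations do not count, and so item 4 settles the matter: the subject is a DLT. The opposite reading, in which item 6 is the complete transaminase rule because it covers both subgroups, also gives a single answer. This stands to the extent that a reader who infers that the same subject both is and is not a DLT goes further than the text. The protocol leaves two readings open, and each is consistent within itself.

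It does not clear the wording. On the literal reading, if g is below 8, the 8×ULN limb can never add a case, and at g = 5 the other limb merely repeats item 4. Item 5, on phosphorus, is different. Persistent values of 7 mg/dL or more can be below Grade 3 on the protocol's own scale (Grade 3 is above 9 mg/dL), so that item catches events that item 4 misses.

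A reader might also infer that sites will send different counts to the same table. The documents support only that they could. The safety monitoring committee includes the principal investigators from each site and the sponsor's medical monitor (Section 7.4.1.3). It reviews all available safety and PK/PD data and takes the table's recommendation into consideration (Section 4.1). A divergent classification could be noticed there, although the protocol gives the committee no rule for resolving it. Finally, the changes in Step 3 would follow from reclassifying any one subject for any reason. They show sensitivity and say nothing about frequency.

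**Conclusion.** The point holds as an internal inconsistency in the DLT definition. Items 4 and 6 are not reconciled, in Section 4.5 or in the synopsis, and the 8×ULN limit either has no effect or conflicts with item 4. The readings diverge over (g, 8]×ULN, which is (5, 8] under the assumption g = 5. That some band exists requires only g < 8, but its width depends entirely on g. Within the band the practical disagreement is mostly confined to events whose Cycle 1 interruption stays under 7 days. A single such event can change an i3+3 recommendation by one step. The number of subjects affected cannot be estimated from the protocol, and nothing here shows that the MTD would be wrong. The correction should be made because every dose assignment uses this count.

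**What to change.** State explicitly which item governs ALT/AST elevations. If item 6 governs, add ALT/AST to the exceptions in item 4. If item 4 governs, remove the limit in item 6 that cannot operate. Use identical wording in Section 4.5 and the synopsis. Which threshold is clinically right is for the sponsor to decide, and this review takes no position on it. The cost is one clause in two places, with no change to the design, the decision algorithm or the sample size.
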